Title: The diagnosis and treatment of *Chlamydia trachomatis* and *Neisseria gonorrhoeae* in pregnant women to prevent adverse neonatal consequences.”

CT/NG to neonates; and 3(c): To assess the frequency and distribution of Sample Adequacy Control (SAC) cycle threshold ( $C_t$ ) values from the Xpert® CT/NG assay, which may be a marker of inflammation, and evaluate correlations with the transmission of CT/NG to neonates.

**Recruitment/Eligibility:** Eligibility criteria for the comparison group are identical to those in Aims 1 and 2. Data will only be collected from participants in the STI testing group.

**Specimen Collection, Transport, Processing and Storage:** A self-collected swab for cytokine measurement will be collected at the baseline, third trimester, and first postnatal care visit and stored at -80°C. A peripheral blood sample (2-4mL) will be collected at the baseline, third trimester, and postnatal study visits. The blood sample will be processed and aliquots of EDTA plasma will be stored at -80°C. The swabs and plasma samples will be transported in dry ice to Stanford University for processing. Luminex will be used to measure the concentrations of 48 cytokines in the 48-plex assay (including IL-1 $\alpha$ , IL-1 $\beta$ , IL-6, IL-7, IL-8, IL-10, granulocyte macrophage colony- stimulating factor [GM-CSF], interferon- $\gamma$  inducible protein [IP]-10, monocyte chemoattractant protein [MCP]-1, MIP-1 $\alpha$ , MIP-1 $\beta$ , and tumor necrosis factor [TNF]- $\alpha$ ). These cytokines were selected based on previously identified associations with genital infection. Additionally the pathogen-specific and SAC Ct results will be automatically generated for each self-collected vaginal sample tested using the Xpert® CT/NG assay at delivery.

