## 5. Characteristics of the Subject Population:

### a. Number of subjects / Sample size:

Pregnant women attending their first ANC care visit at 27 weeks gestation or less. Participants must be 15 years of age and not treated with azithromycin, doxycycline, cefixime, or ceftriaxone in the past 30 days.

**Specific Aim 1 (STI testing group):** We will recruit 250 study participants for CT and NG testing.

**Specific Aim 2 (Standard of care comparison group):** We will recruit 250 antenatal patients from designated study ‘standard of care’ clinics who will be enrolled as a comparison group receiving the standard care with additional IPV and partner services and postnatal care testing (Total N=500). Among participants who test positive during postnatal care, we will offer infant testing (Estimated N=30 infants).

For Specific Aims 1 & 2, study staff will remain at study clinics during operating hours for the duration of the recruitment period. We will consecutively screen all pregnant women for eligibility and offer enrollment to all eligible women.

**Specific Aim 3 (Inflammatory markers):** We will include women in the STI testing group (Estimated N=250).

**Specific Aim 4:** We will enroll an additional 400 antenatal patients for the PoC syphilis sub-study (200 will receive the standard of care and 200 will be offered PoC syphilis testing in addition to the standard of care)

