Statistical Plan: Evaluating the diagnosis and treatment of *Chlamydia trachomatis* and *Neisseria gonorrhoeae* in pregnant women to prevent adverse neonatal consequences in Gaborone, Botswana

ANALYSIS

Primary outcome measure

- Mother-to-child transmission of CT and/or NG: Neonates of mothers who test positive for CT and/or NG infections will be tested using both ocular and nasopharyngeal specimens.

Secondary outcome measures

- Pregnancy outcome
 - o Miscarriage, defined as pregnancy loss before the 20th week of gestation, will be identified through self-report by the participants, and the medical record.
- Perinatal outcome
 - o Stillbirth, defined as fetal death at or after 20 weeks gestation and prior to delivery, will be identified through self-report by the participants, and the medical record.
- Neonatal outcomes
 - o Preterm birth, defined as delivery prior to 37 weeks' gestation, will be identified through the obstetric record and/or
 - o Low birth weight, defined as birth weight of less than 2500g, will be identified through the obstetric record.
 - o Conjunctivitis, defined as the presence of swollen eyelids and pus in eyes, will be identified during the care visit by the follow-up nurse/midwife.
 - o Pneumonia, defined as cough or difficult breathing plus at least one of the following: Fast breathing, Lower chest wall indrawing. In addition, either crackles or pleural rub may be present on chest auscultation.
 - o We will also ask mothers about prior neonatal symptoms and review the obstetric record.
- Maternal outcomes
 - o CT and NG infections: The prevalence of maternal CT/NG infections will be assessed among participants in the testing group at baseline and during the third trimester.
 - o The incidence of infections between baseline and follow-up in the testing group.
 - o Individual cytokines and groups of cytokines associated with mother-to-child transmission of CT/NG, preterm birth, and low birth weight.
- Economic outcomes
 - o The total cost of the CT/NG test and treatment intervention for asymptomatic pregnant women.
 - o The costs per woman tested, treated, and cured; and the incremental costs per adverse neonatal outcome averted (e.g. neonatal CT/NG infections, preterm birth, and low birth weight) comparing the testing intervention with syndromic management.

Statistical analysis

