Prevalence of each STI will be measured as the proportion of individuals testing positive for a given STI divided by the number of individuals tested at each time point. Exact binomial 95% confidence intervals for prevalence will be estimated. Incident infections will be identified when a participant tests negative for an STI during her first ANC visit and positive for an STI during follow-up visits. Time at risk will be the length of time between the first test date and the positive test date. Correlates of CT/NG infections will be identified using both bivariate analyses and multivariate analyses.

Our primary outcome (mother-to-child transmission of CT and NG) and secondary outcomes (composite of preterm birth and/or low birth weight, and prevalence of maternal CT/NG infection at delivery) will be assessed using intention to treat analysis at the clinic level. We will conduct both unadjusted and adjusted analyses, including risk factors for maternal STI and neonatal infection that may be imbalanced between the testing and standard-of-care clinics. Effect measures will be estimated with 95% confidence intervals. All analyses will be carried out using the latest version of Stata statistical software (17.0 or higher; College Station, TX, USA).

To assess immune/inflammatory markers, multiple logistic regression models will be developed in an iterative process to identify individual cytokines and groups of cytokines associated with mother-to-child

transmission of CT/NG, preterm birth, and low birth weight. Additionally, we will identify plasma cytokine signatures that classify study participants with or without preterm birth/low birth weight infants.(1) We will define three equal frequency tertiles or “bins” (low, medium, and high), using all plasma samples. Next, we will use the VSURF R package, a random forest method to select the most predictive cytokines to differentiate samples from participants with and without preterm birth/low birth weight infants.(2) From these, we will build a decision tree to classify the samples. To better calibrate the accuracy of the decision tree, we will perform permutation testing.

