The sample size of 500 participants was determined to have sufficient power to detect a difference in rates of vertical transmission of CT and NG based on 1) the prevalence of CT and/or NG among pregnant women in Botswana (10%),(5) and 2) the risk for vertical transmission of CT/NG to newborn infants during parturition (50%).(49-52). Antenatal CT/NG testing and treatment is expected to reduce vertical transmission by over 85%, from 5% in the control to 0.7% in the intervention group.(49, 50) When accounting for a 7% loss to follow-up rate, 250 women per arm will yield N=232 evaluable subjects. With N=232 evaluable samples per arm, we achieve 80.7% power to detect a 4.3% absolute difference in our primary endpoint, which is the proportion of vertical transmission of CT/NG, between the two groups, using a one-sided Fisher's Exact test, at a 0.05 significance level.

Methods for minimizing bias

Enrollment statistics, including total number of women attending their first antenatal clinic visit, total enrolled, total ineligible, and total who declined to participate, will be recorded in a weekly tally sheet and presented at bimonthly study meetings. Participant characteristics, such as sociodemographic characteristics, gestational age, HIV infection status, syphilis test results, obstetric history (e.g. history of preterm birth), in the testing and standard-of-care clinics will be monitored and compared to assess balance. Attrition will also be monitored and attrition bias will be assessed on a monthly basis.

Data Management

Data will be collected and managed using REDCap electronic data capture tools hosted at the Botswana Harvard AIDS Institute Partnership (BHP). REDCap (Research Electronic Data Capture) is a secure, web-based software platform designed to support data capture for research studies, providing 1) an intuitive interface for validated data capture; 2) audit trails for tracking data manipulation and export procedures; 3) automated export procedures for seamless data downloads to common statistical packages; and 4) procedures for data integration and interoperability with external sources.

Data will be entered offline at study clinics into CRFs on the REDCap mobile application on study tablets. At the end of each working day, data will be checked for any errors, discrepancies and missing data

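### The preterm/low-birth-weight cytokine tree is judged by accuracy alone, which for a minority outcome usually has less power than AUC to detect a real signature

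*SAP*

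**What the plan says.** The SAP's Statistical analysis section, in the text on immune and inflammatory markers, sets out a sequence for preterm birth/low birth weight. Plasma cytokines are cut into tertiles. A random-forest routine (VSURF) is used "to select the most predictive cytokines to differentiate samples from participants with and without preterm birth/low birth weight infants". Then: "From these, we will build a decision tree to classify the samples". The last step is: "To better calibrate the accuracy of the decision tree, we will perform permutation testing".

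Accuracy is the only measure named. The SAP does not say whether it is plain or balanced, or whether it is computed on the same women or by cross-validation. It gives no class weights, rule for labelling a leaf, tree depth, AUC, sensitivity or specificity. Separately, it plans logistic models of individual and grouped cytokines against mother-to-child transmission, preterm birth and low birth weight. Its list of secondary outcome measures includes cytokines associated with those outcomes.

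The Protocol (Study Design, Aim 3) supplies the candidates: "Luminex will be used to measure the concentrations of 48 cytokines in the 48-plex assay". The SAP defines the outcome ("Low birth weight, defined as birth weight of less than 2500g, will be identified through the obstetric record", and similarly delivery before 37 weeks), but neither document gives an expected rate.

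**The concern.** Under the usual majority rule a leaf is labelled affected only if more than half of its women are. If the outcome is uncommon, a cytokine pattern that doubles or triples the risk can still leave every leaf below one half. Splitting on it then changes the predicted risks but not the predicted labels, so accuracy does not move.

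Two things are at stake. The permutation test may fail to find a signature that the same trees would reveal under another statistic. And an accuracy of, say, 85% can look good while being no better than the figure obtained by calling everyone unaffected. Neither problem is cured by permuting the whole procedure correctly, because the weakness lies in the statistic being permuted.

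**Working it through.** **Inputs.** The Protocol (section 5a) expects 250 women in the testing group, the only group giving plasma. The SAP (Sample size) states: "When accounting for a 7% loss to follow-up rate, 250 women per arm will yield N=232 evaluable subjects"; 250 × 0.93 = 232.5, so 232 is used. There are 48 cytokines in tertiles. Assumed, because the documents are silent: outcome rate, signal strength, tree depth, and one plasma sample per woman. The SAP gives no power figure for this analysis, so there is none to reproduce.

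**Step 1: the no-information baseline.** Accuracy when every woman is called unaffected is (232 − affected)/232:

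- 15% (35 affected): 197/232 = 84.9%
- 20% (46): 186/232 = 80.2%
- 25% (58): 174/232 = 75.0%
- 30% (70): 162/232 = 69.8%

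**Step 2: a strong marker that accuracy cannot see.** Take event rates of 5%, 15% and 40% in the low, middle and high tertiles.

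- Overall rate: (5 + 15 + 40)/3 = 20%.
- Odds ratio, high v low: (0.40/0.60)/(0.05/0.95) = 12.7.
- No tertile exceeds 50%, so all three are labelled unaffected. Accuracy = (0.95 + 0.85 + 0.60)/3 = 80.0%, the baseline.
- Labelling the high tertile affected gives sensitivity 40/60 = 67% and specificity (0.95 + 0.85)/2.40 = 75%, but accuracy falls to (0.95 + 0.85 + 0.40)/3 = 73.3%.
- A chi-square test on this single marker (5% level, no correction for the 48 candidates) has over 99% power at n = 232.

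**Step 3: power by accuracy and by AUC.** Simulated data: 232 women, 48 tertile-coded cytokines, one shifted by 0.8 SD in affected women (its own AUC is Φ(0.8/√2) = 0.71). A Gini tree with minimum leaf 7 is scored on the women it was grown on and compared with its no-signal distribution at the 5% level.

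| Outcome rate | Depth 2: accuracy v AUC | Depth 4: accuracy v AUC |
|---|---|---|
| 15% | 11% v 51% | 11% v 22% |
| 20% | 28% v 62% | 14% v 26% |
| 30% | 62% v 81% | 30% v 46% |

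AUC had more power in all 18 settings tried (depths 2, 3 and 4; rates from 15% to 30%; shifts of 0.8 and 1.2 SD). A second depth-4 run gave 18% v 23%, 19% v 34% and 34% v 50%, so single figures can move by up to 8 points while the direction holds. At depth 6 the gap shrinks: 14% v 11%, 13% v 22% and 22% v 32%. Accuracy is thus not behind at 15% there.

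**Step 4: a different design.** Three true markers among 48 correlated ones, the top five carried into a tree of depth up to 4, true joint AUC 0.80:

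| Outcome rate | Cross-validated: accuracy v AUC | Same women: accuracy v AUC |
|---|---|---|
| 15% | 5% v 48% | 25% v 36% |
| 20% | 10% v 61% | 41% v 56% |
| 25% | 20% v 71% | 47% v 66% |
| 30% | 41% v 81% | 65% v 74% |

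In this design, cross-validated balanced accuracy with the cut at the outcome rate recovers most of the gain: 43%, 56%, 67% and 73%. A smaller check with random-forest selection at a 20% rate gave 8%, 28% and 43% by cross-validated accuracy against 47%, 78% and 95% by AUC, at true AUC 0.80, 0.85 and 0.90.

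**The case against.** The best reply is that the SAP leaves accuracy undefined rather than choosing it badly. It could mean balanced accuracy, and nothing rules out class weights or reporting sensitivity. That is fair, but plain accuracy is the ordinary reading, and one clause would settle it.

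A reader might infer that the tree will call nobody affected, so that accuracy ties with its permutation null and sensitivity is near zero. The documents do not support this, because no depth is set. At a 15% rate with a 0.8 SD shift, no woman was called affected in 89% of depth-2 trees but in only 3% of depth-4 trees. The collapse belongs to shallow trees at low rates.

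A reader might also infer that a real signature is usually missed. That too is conditional. In the Step 4 design, cross-validated accuracy finds a signature of true AUC 0.85 in 67% of trials at a 30% rate, and one of 0.90 in 65% at a 25% rate. Nor is every miss due to accuracy: at true AUC 0.75, cross-validated AUC has only 28% to 54% power.

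Permutation already supplies the no-information baseline, so false positives are not inflated and an accuracy of 85% would be tested against the right null. The logistic models do not use accuracy, so the trial does not depend on the tree to find an association. Finally, the simulations use one sample per woman and stand-ins for VSURF, whereas plasma is drawn at three visits. Their sizes are indicative only.

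**Conclusion.** The point holds as a loss of power and a reporting weakness, not as an error that invalidates the analysis. Judging the tree by majority-vote accuracy can miss a signature that AUC would find, most of all at low outcome rates. In the one-marker simulation the loss runs from 19 points (81 − 62, 30% rate) to 40 points (51 − 11, 15% rate) for depth-2 trees, and from 11 to 16 points for depth-4 trees. It is larger under cross-validation and small or absent for deep trees scored on the same women.

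These sizes rest on assumed outcome rates of 15% to 30%, assumed signal strengths, unspecified tree settings and a plain reading of accuracy. The arithmetic in Step 2 needs no simulation, though it is itself an illustrative set of rates. The change is worth making because it is nearly free and the cytokine associations are listed among the secondary outcomes.

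**What to change.** In the SAP's text on immune and inflammatory markers:

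- Replace accuracy with AUC, or with balanced accuracy with the cut at the overall outcome rate, as both the performance measure and the permutation statistic.
- State that cytokine selection and tree fitting are repeated in every permutation, and within each fold if performance is cross-validated.
- Report sensitivity and specificity at a stated cut, and show the no-information accuracy (1 minus the outcome rate) beside any accuracy quoted.
- State the expected preterm/low-birth-weight rate and the tree's depth or pruning rule, so that a reader can judge what the analysis could detect.

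The cost is a few SAP sentences and a few lines of code, with no new data. The price is a headline figure that will look less favourable than raw accuracy.

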To estimate the budget impact of CT/NG testing among asymptomatic pregnant women, we will combine the total recurrent costs with capital, training, and start-up costs. Next, we will build a decision analytic model to estimate the cost per pregnant woman tested, tested positive, treated, and cured by time of delivery. If the intervention is effective, we will calculate the incremental costs per adverse neonatal outcome averted (e.g. neonatal CT/NG infections, preterm birth, and low birth weight) comparing the testing intervention with syndromic management. We will also estimate a cost-effectiveness ratio (ICER, difference in costs divided by difference in health outcomes), representing the change in costs per averted DALYs associated with preterm birth/low birth weight infants.

We will also perform a probabilistic uncertainty analysis where parameters are randomly sampled from probabilistic distributions to generate 10,000 parameter sets. For each parameter set, the model will run and produce a distribution of outcomes. We will provide the means and 95% confidence intervals for all cost and health outcomes. If the intervention is effective, we will also calculate mean incremental cost-effectiveness ratios (ICER; \$/ DALY averted) compared to syndromic management, assessing cost-effectiveness under a willingness-to-pay threshold informed by the WHO's Gross Domestic Product / capita threshold, which was US\$7,961 in Botswana 2019. We will also calculate the probability that the scenarios are cost-effective by assessing the proportion of ICERs that fall below the willingness to pay threshold.(3)

Sensitivity analyses will be conducted through one-way and multi-way methods to identify key cost drivers and assess how changing parameters impacts the overall costs and per patient cost of each strategy.(4)

Sample size

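### Two cost-effectiveness results depend on an undefined finding that the intervention is effective, although the SAP lists one of them as an unconditional secondary outcome

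*SAP*

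**What the plan says.** The economic paragraphs of the SAP's Statistical analysis section attach a condition to two results:

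- Extra cost per adverse outcome prevented: "If the intervention is effective, we will calculate the incremental costs per adverse neonatal outcome averted".
- Mean cost per DALY, judged against a threshold of US$7,961: "If the intervention is effective, we will also calculate mean incremental cost-effectiveness ratios".

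Neither place says which outcome, test or cut-off makes the intervention effective.

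Neighbouring sentences carry no condition in their own wording. One, directly after the first condition, reads: "We will also estimate a cost-effectiveness ratio (ICER, difference in costs divided by difference in health outcomes". The uncertainty analysis reads: "We will also perform a probabilistic uncertainty analysis where parameters are randomly sampled from probabilistic distributions to generate 10,000 parameter sets", followed by "We will provide the means and 95% confidence intervals for all cost and health outcomes". The sentence directly after the second condition reads: "We will also calculate the probability that the scenarios are cost-effective by assessing the proportion of ICERs that fall below the willingness to pay threshold". Budget impact, costs per woman tested, treated and cured, and the sensitivity analyses are also unconditional.

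Under Secondary outcome measures, Economic outcomes, the SAP lists the first gated result with no condition: "and the incremental costs per adverse neonatal outcome averted (e.g. neonatal CT/NG infections, preterm birth, and low birth weight) comparing the testing intervention with syndromic".

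**The concern.** A listed secondary outcome should be reported whatever the trial shows. Here its reporting turns on a judgement made after the data are seen, against a criterion that is not written down.

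Two consequences follow. First, if the model's effect estimate comes from this trial, a ratio that appears only after a favourable result uses an effect that tends to be too large. Cost per outcome prevented has that effect in its denominator, so the reported ratio tends to be too low, which favours testing. Second, when the trial is inconclusive the two results are withheld, although a ministry deciding whether to fund testing would then most want to see cost and effect together with their uncertainty.

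**Working it through.** **1. The two parts of the SAP side by side.**

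| Result | Secondary outcome measures | Statistical analysis |
|---|---|---|
| Extra cost per adverse neonatal outcome prevented | listed, no condition | only if effective |
| Mean cost per DALY against US$7,961 | not listed | only if effective |

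The first row is a contradiction that needs no calculation. In the second, an unconditional ICER sentence stands one paragraph above the conditional one. Whether it and the sentence on the probability of cost-effectiveness inherit the condition cannot be settled from the text.

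**2. Inputs and the plan's own figure.** From the SAP's Sample size section: 5% in the control group, 0.7% with testing, 250 per arm with 7% loss (250 × 0.93 = 232.5, taken as 232), one-sided Fisher's exact test at 0.05, power 80.7%. The plan gives no figure for the economic analysis, so the power is what can be reproduced. With d = 0.043, n = 232 and mean proportion 0.0285:

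- SE under the null = √(0.0285 × 0.9715 × 2/232) = 0.01545
- SE under the alternative = √((0.05 × 0.95 + 0.007 × 0.993)/232) = 0.01532
- z = (0.043 − 1/232 − 1.645 × 0.01545)/0.01532 = 0.867, so power = 80.7%

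The figure reproduces as a continuity-corrected normal approximation. The exact one-sided Fisher test has power 85.2%.

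**3. Size of the selection effect.** Two assumptions are needed that the SAP does not state: a meaning for 'effective', and that the model's effect comes from this trial. All pairs of event counts at 232 per arm were enumerated, and the observed risk difference D was averaged over the trials that pass:

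E[D | pass] = Σ D × P(counts) over passing pairs ÷ P(pass)

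| True rates | True difference (points) | Pass, Fisher p ≤ 0.05 | Mean D if passed | Ratio to truth | Pass, D > 0 | Mean D if passed | Ratio to truth |
|---|---|---|---|---|---|---|---|
| 5% v 0.7% (planned) | 4.3 | 85% | 4.69 | 1.09 | 99.8% | 4.31 | 1.00 |
| 5% v 2% (assumed) | 3.0 | 45% | 4.47 | 1.49 | 95% | 3.17 | 1.06 |
| 5% v 3% (assumed) | 2.0 | 22% | 4.44 | 2.22 | 84% | 2.53 | 1.26 |

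Without a condition the mean of D equals the true difference in every row. Under the Fisher reading, the gated results are withheld in 100 − 85 = 15%, 100 − 45 = 55% and 100 − 22 = 78% of trials.

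**4. Effect on cost per infection prevented.** With incremental cost held fixed, the ratio at the mean passing effect is 1/1.092 = 0.92, 1/1.488 = 0.67 and 1/2.218 = 0.45 of its true value under the Fisher reading. Averaging the ratio itself over passing trials gives 0.98, 0.71 and 0.47, so at the planned effect the understatement nearly vanishes.

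**5. Why deleting the conditions is not sufficient.** ICER = ΔC/ΔE. A draw in which testing costs more (ΔC > 0) and health is worse (ΔE < 0) has a negative ICER. That is below US$7,961, so it would count as cost-effective. A draw with savings and worse health has a positive ICER, for which being below the threshold is unfavourable. Net monetary benefit, NMB = 7,961 × ΔE − ΔC with ΔE in DALYs averted, is negative in the first case and correctly signed in every other.

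**The case against.** The best defence is that a cost per outcome prevented has no meaning when nothing is prevented, so some condition on the ratio is natural. This stands for the ratio. It does not justify withholding the incremental cost and incremental effect from which the ratio is formed; both remain meaningful at a zero or negative effect.

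A second defence is that much of the economic analysis is unconditional. This also stands. A reader might infer that cost-effectiveness as a whole is gated, or that decision-makers would get no answer from an inconclusive trial. The text does not support either: costs, cost per woman cured, and estimates with intervals for cost and health outcomes are due in any event, and by their wording so are one ICER and the probability of cost-effectiveness.

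A third is that the gate truncates nothing. A reader might infer that unfavourable draws are dropped from the 10,000 parameter sets. They are not. The selection lies in whether a given trial reports the result.

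Finally, the larger inflation figures rest on a criterion and on true effects that the SAP does not state. That stands too, and it limits the size that can be claimed. It leaves untouched the conflict within the SAP and the lack of a definition.

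**Conclusion.** The point holds as a minor but real defect: two cost-effectiveness results are gated on an undefined finding, and one conflicts with its own unconditional listing. The gate can bias the reported ratios toward testing. A reader might go further and say that it will overstate value for money by a known amount; the documents do not establish that.

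For neonatal infection, if 'effective' means one-sided Fisher p ≤ 0.05 and the model uses this trial's effect, the mean risk difference among passing trials is inflated by about 9% at the planned effect and 49% at 5% versus 2%. If any favourable point estimate suffices, inflation is about 0% and 6%. The calculation ignores clustering by clinic, for which no intracluster correlation is given. The figures do not apply directly to the cost-per-DALY ratio, because the SAP ties those DALYs to preterm birth and low birth weight, whereas the power calculation concerns vertical transmission.

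**What to change.** Delete both conditions, which also brings the analysis text into line with the listed secondary outcome. In their place, state that:

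1. Incremental cost and incremental effect will be reported with joint uncertainty from the planned 10,000 parameter sets, whatever the primary result.
2. The probability of cost-effectiveness will be the proportion of draws with positive net monetary benefit, at US$7,961 per DALY averted and over a range of thresholds, in place of the proportion of ICERs below the threshold.
3. A ratio will be given only where the incremental effect is positive enough to interpret, by a rule written down in advance. This is harmless once items 1 and 2 are always reported.

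The SAP should also say whether the model's effect parameters come from this trial.

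The cost is small: a few sentences and slightly more analysis and reporting, from a model and draws that are already planned. The sponsor also accepts that the published cost-effectiveness result may be less favourable.

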#### 4. Background and Significance

*Chlamydia trachomatis* (CT), *Neisseria gonorrhoeae* (NG) and syphilis (caused by *Treponema pallidum*) infections are bacterial STIs that cause adverse neonatal outcomes. The risk of vertical

Title: The diagnosis and treatment of *Chlamydia trachomatis* and *Neisseria gonorrhoeae* in pregnant women to prevent adverse neonatal consequences.”

transmission of CT/NG during delivery is about 50%. Among infants born to mothers with untreated CT infection, 30–50% develop clinical conjunctivitis and 10-20% develop pneumonia due to CT. Among infants born to mothers with untreated NG infection, the risk of conjunctival infection is up to 48%, which can result in corneal damage and blindness. A recent study in South Africa found that among infants born to a mother with CT, NG, or *Trichomonas vaginalis* (TV) infections, 37% had nasopharyngeal colonization with the same STI organism. Other studies on CT/NG infections in neonates are over 20 years old. HIV-infected pregnant women with CT/NG infections are at increased risk of MTCT of HIV. Untreated syphilis during pregnancy is associated with increased risk for early fetal death, stillbirth, preterm birth, low birthweight, neonatal death, and clinical disease in infants. Congenital syphilis is the second leading cause of preventable stillbirth globally.

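### The only DALYs the SAP defines for its ICER come from preterm birth and low birth weight, so the threshold test gives no health credit for averted neonatal CT/NG infection or its sequelae

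*SAP*

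**What the plan says.** The SAP's primary outcome is "Mother-to-child transmission of CT and/or NG", and its Sample size section rests on that outcome alone. Neonatal conjunctivitis and pneumonia are listed as secondary outcomes, alongside miscarriage, stillbirth, preterm birth and low birth weight. Protocol Section 4 presents conjunctivitis and pneumonia as harms of untreated infection: among infants of mothers with untreated CT, "30–50% develop clinical conjunctivitis and 10-20% develop pneumonia due to CT". For untreated NG it gives a conjunctival infection risk of up to 48%.

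The economic paragraphs of the SAP's Statistical analysis section contain two measures of value for money:

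- A natural-unit measure: "incremental costs per adverse neonatal outcome averted (e.g. neonatal CT/NG infections, preterm birth, and low birth weight". It includes neonatal infection and has no threshold attached.
- A DALY-based ICER, described as "representing the change in costs per averted DALYs associated with preterm birth/low birth weight infants". This is the only place where the SAP says which outcomes generate DALYs.

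The next paragraph says that, if the intervention is effective, "we will also calculate mean incremental cost-effectiveness ratios (ICER; \$/ DALY averted) compared to syndromic management". The comparison is with a willingness-to-pay "threshold informed by the WHO's Gross Domestic Product / capita threshold, which was US\$7,961 in Botswana 2019", and the probability of cost-effectiveness comes from "assessing the proportion of ICERs that fall below the willingness to pay threshold". The one-way and multi-way sensitivity analyses are meant to find cost drivers and to "assess how changing parameters impacts the overall costs and per patient cost of each strategy". No alternative DALY scope is planned.

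**The concern.** The intervention is meant to work mainly by preventing transmission to the newborn. The trial is sized on that effect, and the protocol's rationale leans on the eye and lung disease that follows. The one economic measure that is compared with a threshold takes its health gain from a different place, preterm birth and low birth weight, for which the trial was not sized.

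Two things follow if the wording is applied literally. First, a real benefit of testing is left out of the denominator, which pushes cost per DALY averted upward. Second, the SAP does not say on which outcome the intervention must be effective before the ICER is calculated. A clear effect on transmission could therefore trigger an ICER whose denominator is a preterm/low-birth-weight effect close to zero.

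**Working it through.** **1. The SAP's own design figures (Sample size).** Maternal prevalence 10% × transmission risk 50% = 5% in the control group. The intervention rate is 0.7%. Absolute difference: 5% − 0.7% = 4.3 percentage points. Relative reduction: 1 − 0.007/0.05 = 0.86, which agrees with the stated reduction of over 85%. The stated 80.7% power at 232 per arm is for this outcome. A one-sided pooled normal approximation with continuity correction gives 80.69%, whereas exact enumeration of the one-sided Fisher test gives 85.2%. That difference does not affect this point.

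**2. Health gain with no DALY credit.** Infections averted per 1,000 women = 1,000 × (0.05 − 0.007) = 43, or 232 × 0.043 ≈ 10 in an arm of 232.

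**3. Sequelae, as an illustration.** Assumptions: all maternal CT/NG infections carry the protocol's risks for untreated CT, and sequelae fall by the same 86% as transmission. With 1,000 × 0.10 = 100 infected mothers:

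- conjunctivitis averted: 100 × (0.30 to 0.50) × 0.86 = 25.8 to 43.0
- pneumonia averted: 100 × (0.10 to 0.20) × 0.86 = 8.6 to 17.2

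These counts overlap with the 43 infections, because sequelae arise in infected infants. They must not be added to it, and they are cases, not DALYs.

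**4. Effect on the ICER.** Let ΔC be the incremental cost (positive and held fixed), D_r the averted DALYs from preterm birth/low birth weight, D_o the omitted averted DALYs, and s = D_o/(D_r + D_o). Then

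restricted ICER = ΔC/D_r = [ΔC/(D_r + D_o)] × 1/(1 − s).

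The documents give no value for s, so the range below is assumed. The last column is the full-scope ICER at which the restricted ICER would sit exactly at the threshold, 7,961 × (1 − s).

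| s (assumed) | Overstatement 1/(1 − s) | Full-scope ICER, US$ |
|---|---|---|
| 10% | 1.11 | 7,165 |
| 25% | 1.33 | 5,971 |
| 50% | 2.00 | 3,981 |
| 75% | 4.00 | 1,990 |

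**5. The same question in money.** Suppose each averted transmission carries w DALYs through its sequelae (assumed). The omitted gain is then worth 43 × w × 7,961 / 1,000 per woman at the threshold: US$1.71 for w = 0.005, US$3.42 for w = 0.01 and US$34.23 for w = 0.1. The omission can therefore be trivial or material, depending on inputs that the documents do not give.

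**6. Near-zero denominator.** As D_r approaches 0, s approaches 1 and the factor 1/(1 − s) has no bound. In the planned 10,000 draws, D_r may also change sign. A draw with higher cost and negative DALYs averted gives a negative ratio, which literally lies below US$7,961 and would count as cost-effective. Instability can thus mislead in either direction.

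**The case against.** The strongest reply is that the threshold sentence does not repeat the restriction. It speaks only of DALYs averted, and its paragraph promises results for all cost and health outcomes, so a wider scope may have been intended. That is possible. But the restricted definition is the only one in the SAP, and an analyst who follows the text would use it. If a wider scope was meant, the text still has to say so.

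It can also be said that choosing which outcomes generate DALYs is a modelling choice, that the restriction is conservative against testing, and that conjunctivitis and pneumonia are not outcomes the trial was sized for either. All of this is fair. It argues for stating and justifying the scope and for showing results under both scopes; the SAP does neither.

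A reader might infer more than the documents support:

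- *That the primary outcome counts for nothing in the economic evaluation.* It is credited in the cost per adverse neonatal outcome averted, which is a listed economic outcome. The gap is confined to the DALY ICER and the threshold test.
- *That adoption depends on this ICER alone.* Neither document says so, and the DALY ICER is not in the SAP's list of economic outcomes.
- *That the numerator carries the whole cost of testing.* It is a difference in costs, and nothing excludes savings from avoided neonatal care.
- *That an infant who is both preterm and of low birth weight is counted twice.* The listed outcomes can be read as separate ratios, and the statistical section already uses a composite of the two.

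**Conclusion.** The point holds in this limited form. As written, the DALY ICER and the probability of being cost-effective omit the health gain from averted neonatal CT/NG infection and its sequelae. At the SAP's rates that is about 43 averted infections per 1,000 women with no DALY credit. Given positive incremental cost held fixed and a positive preterm/low-birth-weight effect, the direction is against testing. If that effect is near zero, the ratio is unstable.

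The size of the shift in the ICER is unknown. It depends on disability weights, durations and costs that the documents do not give, and it could be small if sequelae are mild and treated, as the protocol provides for infants who test positive. The primary analysis and the clinical secondary analyses are unaffected.

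**What to change.** In the economic part of the SAP's Statistical analysis section, define base-case DALYs averted as the sum of two components:

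1. DALYs from preterm birth/low birth weight, counted once per infant by using the composite already defined in that section.
2. DALYs from the sequelae of neonatal CT/NG infection, namely conjunctivitis and pneumonia, without adding a further weight for the infection itself.

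Use this scope for the US$7,961 comparison and for the probability of being cost-effective. Report the preterm/low-birth-weight-only ICER as a scenario analysis. Stillbirth, already a listed SAP outcome, may be a further scenario.

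The cost is SAP wording and a few more literature parameters in a model still to be built, with no new data collection. The added uncertainty can be carried through the planned 10,000-draw analysis.
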